The most effective and durable treatment for both obesity and type 2 diabetes mellitus (T2DM) remains bariatric surgery. Alternative surgical techniques have been sought to improve the rates of T2DM remission. Standard Limb RYGB and biliopancreatic diversion (BPD) has been showed to lead to a matched total body weight loss of 33% at 2 years post-operatively. Unfortunately, the BPD procedure has the distinct disadvantage of a substantially higher risk of developing severe nutritional complications, and this has limited its use.

To improve the glucose-lowering efficacy of Standard Limb RYGB, whilst avoiding the high risk of complications with the BPD procedure, the Long Limb RYGB has been devised as a hybrid operation that combines the standard design of Standard Limb RYGB, but with a longer biliopancreatic limb. Previous research has suggested that the rates of any complications, including nutritional, were not higher than those reported after Standard Limb RYGB.

The main anatomical difference between Long Limb RYGB and Standard Limb RYGB is that the segment of the bypassed proximal intestine, the biliopancreatic limb, is longer (150 vs. 50cm respectively). This means that in the Long Limb RYGB the common channel is shorter, and as a result nutrients reach the distal small bowel faster and in a less-digested state. The hypothesis is that the Long Limb RYGB is better for treatment of T2DM because: a) It increases post-prandial secretion of gut hormones, and in particular glucagon-like peptide-1 (GLP-1) which results in the immediate post-prandial insulin secretion significantly higher than the Standard Limb RYGB.

b) It increases insulin sensitivity significantly more than the Standard Limb RYGB, before and after weight loss has taken place.

The trial will evaluate the efficacy on T2DM of the Long Limb RYGB compared to the Standard Limb RYGB, and investigate the mechanisms underlying any potential differences by conducting:

- 1. Mechanistic assessments with Mixed Meal Tolerance Test (MMTT) and Hyperinsulinaemic Euglycaemic Clamp at: pre-operative, early mechanistic postoperative (at 1-2 weeks after the surgery) and late mechanistic post-operative visits (at 20% total body weight loss after the surgery).
- 2. Clinical assessment pre-operatively, at the day of surgery and at 3, 6 and 12 months post-operatively.

4 Study Methods

4.1 General Study Design and Plan

The study is a prospective double-blinded randomised controlled parallel group clinical trial. Patients were recruited from the Imperial Weight Centre and the King's College Obesity Clinic and randomised to either the Long Limb or the Standard Limb RYGB surgery.

4.2 Inclusion-Exclusion Criteria

4.2.1 Inclusion Criteria

The participants must have met ALL of the following criteria to be considered eligible for the study:

- Male or female participants
- Aged between 18-70 years
- Diagnosed with T2DM according to WHO 2006 and 2011 criteria
- HbA1c \geq 7.0% (\geq 53.0 mmol/mol) on screening
- Body mass index (BMI) \ge 30 kg/m² and eligible for bariatric surgery based on NICE guidance
- On glucose-lowering medications
- Willing to comply with study requirements and able to give informed consent

4.2.2 Exclusion Criteria

Participants were not allowed to enter the study if ANY of the following applied:

- History of any medical, psychological or other condition, or use of any medications, including over-the-counter products, which, in the opinion of the investigators, would either interfere with the study or potentially cause harm to the volunteer.
- Without access at home to a telephone or other factor likely to interfere with ability to participate reliably in the study.
- Specific contraindications to bariatric surgery
- Previous bariatric surgery
- Diagnosed with Type 1 diabetes mellitus
- Donated blood during the preceding 3 months or intention to do so before the end of the study Current pregnancy or breastfeeding
- Inability to maintain adequate contraception

4.3 Randomisation and Blinding

Participants were randomised to Long Limb or Standard Limb RYGB surgery in a 1:1 ratio. All patients were randomised in a single stratum.

4.4 Study Variables

4.4.1 Summary of study data and timing of measurements

The study measured patients at the following timepoints:

- Screening
- Pre-operative mechanistic visit
- Day of the operation

- Early mechanistic post-operative visit 1-2 weeks after operation
- Late mechanistic post-operative visit at 20% total body weight loss of the preoperative value
- 3 months post-operatively
- 6 months post-operatively
- 12 months post-operatively

Table 1 outlines the key study measurements, and the timing of these measurements.

	Screening visit	Pre-op visit	Operation	Early mechanistic post-op visit	Late mechanistic post-op visit	3, 6 months post-op	12 months post-op
Demographics, duration of T2DM	Х						
Weight/weight loss, BMI			х			Х	х
HbA1c			х			х	х
Other blood tests			Х				х
BP /heart rate	х	Х		х	х		х
Body composition and measurements, BMR	x	Х		x	X		х
Comorbidities and King's Score	х						Х
Medications			Х			Х	х
Food diary		Х		Х	Х		
Rates of T2DM remission							Х
Bowel movements							х
GLP-1, GIP, PYY, bile acids, FGFs		Х		X	х		
Fasting Plasma Glucose		Х	x	x	х		х
Postprandial plasma glucose		Х		х	х		
Markers of insulin secretion		Х		х	х		
Ra, Rd, MCR from Clamp		Х		x	х		
VAS		Х		Х	Х		
Microbiota, metabolomics		Х		X	Х		
Faecal calories		Х					х
Adverse events							х

5 Sample Size

The sample size was based on the primary outcome, GLP-1 concentration after the Mixed Meal Tolerance Test.

The study was powered to detect a difference in peak of active GLP-1 of 10.0 pmol/L, equating to the previously estimated change in GLP-1 post-surgery in the Standard Limb RYGB group. The standard deviation of the change in outcome values was estimated to be

10.8 pmol/L within each group. It is calculated that, with a 5% significance level and 90% power, a sample size of 20 patients in each arm was required. Based on experience, it was estimated that up to 20% of patients will drop-out of the study. To allow for this, 25 patients in each arm of the trial were planned, 50 patients in total.

6 Study Objectives and Endpoints

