9.1 Primary Efficacy Analysis

The primary endpoint of the study is the peak of active GLP-1 concentration at the early mechanistic post-op visit.

The analysis will be performed using Analysis of Covariance (ANCOVA). In the analysis, the peak of active GLP-1 concentration at the early mechanistic post-operative visit will be considered as the outcome measure, whilst baseline peak of active GLP-1 will be included as a covariate.

If the data does not meet the assumptions of the ANCOVA analysis (e.g. normally distributed residuals, homogeneity of variance), a data transformation of the outcome variable (e.g. log transformation) before analysis will be utilised to ensure that the assumptions are met.

The summary statistics for the outcome variable will be produced in accordance with section 8.2. The baseline adjusted difference in outcome values between groups will be reported, along with a corresponding 95% confidence interval.

The primary study analysis will be performed using the Full Analysis Population (see section 7.2.1).

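### The 20 per arm at 90% power in SAP section 5 does not follow from its inputs for the two-sided 5% inference implied by section 9.1, and section 5 states no sidedness

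*SAP*

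**What the plan says.** SAP section 5 gives these inputs and results:

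- Target difference: "The study was powered to detect a difference in peak of active GLP-1 of 10.0 pmol/L".
- Variability: "The standard deviation of the change in outcome values was estimated to be" "10.8 pmol/L within each group". This is an SD of change, not of the post-operative value.
- Result: "It is calculated that, with a 5% significance level and 90% power, a sample size of 20 patients in each arm was required".
- After an allowance for up to 20% drop-out: "To allow for this, 25 patients in each arm of the trial were planned, 50 patients in total".

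The section names no test or formula and gives no sidedness and no pre/post correlation.

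SAP section 9.1 analyses the post-operative peak by ANCOVA with the baseline peak as covariate. On reporting it says: "The baseline adjusted difference in outcome values between groups will be reported, along with a corresponding 95% confidence interval". The SAP nowhere mentions a one-sided test.

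**The concern.** A 95% confidence interval excludes zero exactly when a two-sided 5% test rejects. A sample size meant to support that interval should therefore use a two-sided 5% level. With the section 5 inputs, that level and 90% power give a number clearly above 20.

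What is at stake is how the primary result is read. If it is not significant, the 90% figure tells the reader that a true difference of 10.0 pmol/L would have been missed one time in ten. On the inputs that section 5 itself uses, with no baseline adjustment, that chance is nearer one in five at 20 evaluable per arm. The estimate and its interval are unaffected.

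**Working it through.** **Inputs.** Difference 10.0, SD of change 10.8, level 5%, power 90%, drop-out 20% (all section 5); 1:1 allocation (section 4.3); 95% interval (section 9.1).

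**Formula.** For two equal groups, normal approximation:

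n per arm = 2 × (z_α + z_β)² × (SD/difference)², with 2 × (10.8/10.0)² = 2.3328.

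**Reproducing the plan's figure**

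| Level | Power | (z_α + z_β)² | n, normal | n, t-test |
|---|---|---|---|---|
| One-sided 5% | 90% | (1.645 + 1.282)² ≈ 8.564 | 19.98 → 20 | 21 |
| Two-sided 5% | 80% | (1.960 + 0.842)² ≈ 7.849 | 18.31 → 19 | 20 |
| Two-sided 5% | 90% | (1.960 + 1.282)² ≈ 10.507 | 24.51 → 25 | 26 |

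(Squares computed from unrounded z values; the t-test column uses the noncentral t distribution.)

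The printed 20 appears in the first row (normal formula) and the second row (t-test). It does not appear in the third, which is the row that matches a 95% interval and the stated 90% power.

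**Drop-out step.** 20/(1 − 0.20) = 25. This step is correct, given 20.

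**Power for an unadjusted comparison of change scores, difference 10.0, SD 10.8**

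| Evaluable per arm | Two-sided, t | Two-sided, normal | One-sided, t | One-sided, normal |
|---|---|---|---|---|
| 20 | 81.4% | 83.3% | 89.1% | 90.0% |
| 25 | 89.4% | 90.6% | 94.3% | 94.8% |
| 26 | 90.6% | 91.6% | 95.0% | 95.5% |

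The difference detectable with 90% power at 20 per arm (two-sided t-test) is 11.36, or about 11.4 pmol/L.

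**Effect of the planned ANCOVA.** Assume equal variances before and after surgery and pre/post correlation ρ; neither is given in the SAP. With common variance σ², the change has variance 2σ²(1 − ρ) and the ANCOVA residual has variance σ²(1 − ρ²). The ratio is (1 + ρ)/2, so the residual SD = 10.8 × √((1 + ρ)/2). Two-sided power at 20 per arm, t distribution:

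| ρ | Residual SD | Power |
|---|---|---|
| 0.3 | 8.71 | 94% |
| 0.5 | 9.35 | 91% |
| 0.7 | 9.96 | 87% |
| 0.9 | 10.53 | 83% |

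Power crosses 90% at ρ of about 0.55.

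**The case against.** **Sidedness is not a stated input.** Section 5 says only 5%. At one-sided 5% the normal formula gives 20, and the drop-out step then gives 25, so both printed figures reproduce. The SAP's background hypothesis is also directional: it expects the long limb to raise GLP-1 more. A reader might infer from the two-sided result that 20 is a plain arithmetic slip. The document does not support that, and this part of the objection stands. But it does not reconcile the two sections. No one-sided test is announced, the objective in section 6.1 is simply to compare the procedures, and a one-sided 5% test would pair with a 90% interval rather than the planned 95% one.

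**The planned analysis is ANCOVA, not a t-test on change scores.** This also stands. A reader might infer that the trial has only 81% power, or that its type II error is certainly about twice the implied 10%. The SAP does not allow that conclusion. Under equal variances, 81% is roughly the floor reached as ρ approaches 1, and lower correlations give more power, including 90% or above. The true power is undetermined because no correlation is given. Equally, section 5 does not invoke baseline adjustment, so ANCOVA does not explain how 20 was obtained.

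**Twenty evaluable is a worst case.** Section 5 allows for up to 20% loss from a study lasting 12 months, while the primary measurement is at 1–2 weeks. If all 25 per arm are evaluable, unadjusted two-sided power is 89.4% (t) or 90.6% (normal), close to the claim. This is fair. But section 5 attaches the 90% to 20 per arm, not 25.

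**Conclusion.** Wrong as written, of moderate importance. The stated 90% power at 20 per arm does not follow from the section 5 inputs for the two-sided 5% inference implied by section 9.1. That inference needs 25 per arm (normal) or 26 (t-test) without baseline adjustment. At 20 evaluable per arm the unadjusted power is 81.4% (t) or 83.3% (normal), against the stated 90%.

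The conclusion rests on reading the 95% interval as a two-sided 5% test, and on taking section 5 at face value as an unadjusted comparison using the SD of change. It does not establish that the trial is underpowered, since the ANCOVA could make up the shortfall at a pre/post correlation of about 0.55 or lower (equal variances assumed). The correction changes the stated power and how a null primary result should be read. It changes no estimate, test or analysis population.

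**What to change.** In SAP section 5, state that the 5% level is two-sided and replace the power statement with text such as:

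*For an unadjusted two-sided 5% comparison of change scores (difference 10.0 pmol/L, SD 10.8 pmol/L), power is about 81% with 20 evaluable patients per arm and about 89% with all 25 evaluable per arm. The difference detectable with 90% power at 20 per arm is 11.4 pmol/L.*

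If the efficiency of the ANCOVA is relied on, add the assumed pre/post correlation, its source, and the resulting power. Assuming equal variances, at 20 per arm this is about 91% at a correlation of 0.5, 87% at 0.7 and 83% at 0.9. If a one-sided test was in fact intended, say so and reconcile it with the 95% interval in section 9.1.

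The cost is a few sentences in the SAP and a less favourable power figure. No extra patients are asked for; the SAP already describes recruitment and randomisation in the past tense.

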6.1 Study Objectives

The study will assess the following research questions:

The primary objective is to compare Long Limb and Standard Limb RYGB in terms of the change in peak of active GLP-1 concentration after the mixed meal tolerance test 1-2 weeks after the surgery.

The secondary objectives are to compare Long Limb and Standard Limb RYGB in terms of a number of other efficacy outcomes, and also to compare surgical methods in terms of their safety.

6.2 Demographic and Baseline measurements

The following demographic and baseline characteristics of the study participants will be collected:

- Age
- Gender
- Ethnicity
- Duration of T2DM
- Height

6.3 Endpoints

6.3.1 Primary outcome measure

The primary study endpoint is:

• Peak of active GLP-1 concentration after the mixed meal tolerance test 1-2 weeks after the surgery.

6.3.2 Secondary outcome measures

The secondary endpoints are measured at several different timepoints.

Endpoints from mixed meal test at late mechanistic post-operative visit:

• Peak of active GLP-1 concentration

Endpoints from both early and late mechanistic post-operative visits:

- a) From the Hyperinsulinaemic Euglycaemic Clamp
 - Rate of glucose appearance (Ra) and disposal (Rd) and metabolic clearance rate of glucose (MCR) basal, low and high
- b) From the MMTT:
 - Active GLP-1 concentration (AUC)
 - Total GLP-1 (peak, AUC)
 - PYY (peak, AUC)
 - GIP (peak, AUC)
 - Markers of insulin secretion (peak, AUC)
 - Plasma glucose (peak, AUC)
 - Bile acids (peak, AUC)
 - FGF-19 and 21 (peak, AUC)
 - Systolic and diastolic blood pressure (AUC)
 - Heart rate (AUC)
 - Appetite ratings (Visual Analogue Scales; AUC)
- c) Blood, urine and faecal microbial diversity and metabolomics
- d) Total caloric intake and macronutrient composition % fat, % protein, % carbohydrates
- e) Body composition and Basic Metabolic Rate (BMR)

Endpoints at the day of surgery:

- Common channel length
- Total small bowel length
- Proportion of common channel to total small bowel length
- Operating time
- Length of in hospital stay

Endpoints at 3, 6 and 12 months:

- HbA1c
- % of total body weight loss
- Number of glucose lowering medications

Secondary endpoints at 12 months:

- % of total body weight loss
- BMI
- Body composition
- Basic Metabolic Rate (BMR)
- Waist, hips and neck measurements
- T2DM remission
- Comorbidities
- Medications
- King's Obesity Staging Score
- Systolic and diastolic blood pressure
- Heart rate
- Oxygen saturation
- Bowel movements frequency

- Blood tests: fasting plasma lipids concentration, fasting plasma glucose, haematinics, vitamins
- Total caloric intake
- Macronutrient composition % fat, % protein, % carbohydrates
- Faecal caloric content

6.3.3 Safety outcomes

Safety will be assessed by the recording of adverse events (AEs) and serious adverse events (SAEs) reported during the operation for up to one-year following surgery. This will include medical, surgical, nutritional and psychological complications adverse events.

An SAE will be defined as an adverse event that meets any of the follow criteria:

- Leading to death
- Life-threatening
- Leads to hospitalisation or prolongation of existing hospitalisation
- Persistent or significant disability or incapacity
- Congenital anomaly or birth defect.

6.4 Derived values

Peak

For each outcome, the peak will be defined as the maximum post-meal concentration (i.e. from time 15 onwards) per patient, regardless of at which timepoint the peak concentration was achieved.

Area Under the curve (AUC)

A number of outcomes from the mixed-meal tests will be summarised by the Area under the curve values. The AUC will be calculated using the trapezium rule.

For outcomes with measurements at time -30, the first value used in the calculation will be the mean of the -30 and 0 timepoints. When there is no -30 value, the time 0 value will be used as the first measurement in the calculation.

Absolute changes from baseline

Absolute changes from baseline will be calculated by subtracting the individual subject's baseline value from the value at the outcome timepoint.

Percentage changes from baseline

Percentage changes from baseline will be calculated by subtracting the individual subject's baseline value from the value at the outcome timepoint, dividing this sum by the baseline value and multiplying by 100.

7 General Considerations

7.1 Timing of Analyses

A single analysis will take place at the completion of the study, after all data is collected. No interim analyses will be performed.

7.2 Analysis Populations

7.2.1 Full Analysis Population

The Full Analysis Population will consist of patients in the groups to which they were randomised, regardless of deviation from the protocol or whether they received the allocated surgery. Patients with completely missing data at the outcome timepoint will be excluded from this dataset for the particular outcome for which they had missing data.

7.2.2 Per Protocol Population

The Per Protocol patient population will consist of those patients who received the surgery that they were randomised to. Patients receiving surgery different to their allocation will be excluded from this population. Analyses will only be performed using this population if it differs from the Full Analysis Population.

7.2.3 Safety Population

The safety population will consist of all patients recruited into the study who participate for at least one week of the study. This dataset will analyse patients in the groups to which they were randomised, regardless of deviation from the protocol or whether they received the allocated surgery.

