9.3 Sensitivity Efficacy Analysis

If the Per Protocol Population differs in its membership from the Full Analysis Population, the primary outcome will be additionally analysed using this population. The analysis methods will be equivalent to those described in Section 9.1.

If there is no difference between the Per Protocol Population and Full Analysis Population, no sensitivity analyses will be performed.

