9.4 Other Analyses

An additional set of analyses will examine the association between the key primary and secondary efficacy outcomes measured on a continuous scale and the proportion of the common channel length to the total small bowel length. The analysis will be performed using Pearson correlation. Alternatively, Spearman's rank correlation will be used if the Pearson correlation assumptions (e.g. non-linear relationship, both variables non-normally distributed) are not met. For each outcome, a single analysis will be performed for all patients, combining the two study arms together.

10 Safety Analyses

The main safety outcome is the occurrence of adverse events (AEs). For each of the study groups, the number of adverse events in each group and per patient will be summarised. Specific details of the adverse events will be recorded in addition to the number of AEs that are serious and non-serious.

If it is deemed that there are sufficient occurrences of adverse events in total, a formal test of significance will be performed to compare AE occurrence at the patient level between study arms. Fisher's exact test will be used for this analysis. However, it is acknowledged that the study is unlikely to be powered to show a difference between groups for this endpoint.

11 Technical Details

The data analysis will be primary performed using the statistical software packages Stata (version 15.1), SPSS (version 20 or later), GraphPad PRISM (version 6 or later). Programs recording details of all data manipulation and data analyses will be produced and kept, so that the analyses can be externally inspected and, if necessary, re-run.

The exception is for the analysis of the blood, urine and faecal microbial diversity and metabolomics outcomes, which will be analysed using the Vegan library within the R statistical package and the Statistical Analysis of Metagenomic Profiles software package.

12 Summary of Changes to the Analysis Plan

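### The safety population has an undefined one-week entry rule and groups patients as randomised, so its rates depend on an unstated choice and a patient given the other operation is counted under one not performed

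*SAP*

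**What the plan says.** Section 7.2.3 sets two rules for the safety population.

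- **Entry:** "The safety population will consist of all patients recruited into the study who participate for at least one week of the study". The section does not say whether the week is counted from recruitment, randomisation or surgery.
- **Grouping:** "This dataset will analyse patients in the groups to which they were randomised", and this applies "regardless of deviation from the protocol or whether they received the allocated surgery".

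Four other places bear on these rules.

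- Section 6.3.3 covers adverse events "reported during the operation for up to one-year following surgery". Its criteria for a serious event include death and life-threatening events.
- Section 6.1 makes a safety comparison of the surgical methods a secondary objective.
- Section 7.2.2 foresees that a patient may have the other operation: "Patients receiving surgery different to their allocation will be excluded from this population". Section 9.3 uses that per-protocol population for one purpose only: "the primary outcome will be additionally analysed using this population".
- Section 10 summarises adverse events by study group and per patient. It does not name the population it uses.

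**The concern.** A safety population for a comparison of two operations should contain the patients exposed to those operations, from the moment exposure starts. Section 7.2.3 ties membership to length of participation instead, and the starting point is open. Each way of closing that gap gives a set of patients that does not match the event window in section 6.3.3. The choice would have to be made at analysis, and section 7.1 places the only analysis after all data are collected.

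The grouping rule is a separate problem. Operative and nutritional complications come from the anatomy actually created. When a patient had the other operation, analysis by allocation puts those complications in the wrong column and pulls the two arms together. For a safety comparison, that is the direction that hides a difference.

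At stake is whether the adverse event table describes the operations it is labelled with and whether it contains every patient who had one.

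**Working it through.** The SAP gives no adverse event rate, early-exit count or crossover count, so there is no stated safety figure to reproduce. The only document figure used is the planned arm size in section 5: 20 per arm, allowing for 20% drop-out, is 20 / (1 − 0.20) = 25 per arm, which matches the SAP. All event and crossover counts below are assumptions for illustration.

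**1. Week counted from surgery.** A patient who dies or stops participating within 7 days leaves both numerator and denominator. If x of 25 patients have an event and k of those x exit in the first week, the reported rate changes from x/25 to (x − k)/(25 − k).

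| Assumed x | k | Full rate | Reported rate |
|---|---|---|---|
| 1 | 1 | 1/25 = 4.0% | 0/24 = 0% |
| 5 | 1 | 5/25 = 20.0% | 4/24 = 16.7% |
| 5 | 2 | 5/25 = 20.0% | 3/23 = 13.0% |
| 5 | 3 | 5/25 = 20.0% | 2/22 = 9.1% |

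For the first row, the exact (Clopper-Pearson) 95% interval for 1/25 is 0.1% to 20.4%. For 0/24 the upper limit is 1 − 0.025^(1/24) = 14.2%. A patient with a first-week event who stays in the study is counted, so k covers only those who die or leave.

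**2. Week counted from recruitment.** Operated patients will probably have qualified by the day of surgery, since section 4.4.1 lists a screening visit and a pre-operative visit beforehand. The interval is not given, so this too is an assumption. However, a patient who was recruited, took part for a week and was never operated on also qualifies, although events are counted only from the operation. If m of 25 are never operated on and 5 of the rest have an event, the rate among operated patients is 5/(25 − m), but the reported rate is 5/25 = 20.0%.

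- m = 1: 5/24 = 20.8%
- m = 2: 5/23 = 21.7%
- m = 3: 5/22 = 22.7%

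The section also admits patients who are recruited but analyses them as randomised. A patient who was recruited and never randomised has no group.

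**3. Grouping as randomised.** Let the true event rates by operation received be pL and pS, and let c of 25 patients allocated to Long Limb receive Standard Limb. The expected difference by allocation is

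[(25 − c)/25 × pL + c/25 × pS] − pS = (25 − c)/25 × (pL − pS).

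With assumed rates of 30% and 10%, a true difference of 20 points:

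| c | Expected difference (points) |
|---|---|
| 1 | 24/25 × 20 = 19.2 |
| 2 | 23/25 × 20 = 18.4 |
| 3 | 22/25 × 20 = 17.6 |
| 5 | 20/25 × 20 = 16.0 |

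**4. Is it repaired elsewhere?** The per-protocol population would remove crossovers, but section 9.3 applies it to the primary outcome only. Section 10 reports by study group. No safety analysis by operation received appears anywhere in the SAP.

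**The case against.** The best defence is that section 7.2.3 speaks of a week of the study, not a week after surgery. With two pre-operative visits in the schedule, most patients could satisfy it before the operation, and then no peri-operative death or withdrawal is lost. Even on the other reading the loss is narrow, because only death or departure within 7 days removes a patient. Such an exit would still appear in the CONSORT diagram and the withdrawal reasons required by section 8.1. Crossover is mentioned only as a possibility, and its effect is small beside an interval as wide as 0.1% to 20.4%.

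Most of this stands, and it limits the point. A reader might infer that the plan does exclude peri-operative deaths and so makes both operations look safer than they are. The SAP does not support that: the start of the week is undefined, and the loss follows only if it runs from surgery. What the defence does not do is rescue the definition. The reading that keeps early deaths in is the one that lets in patients never operated on. A patient listed in the CONSORT diagram but absent from the adverse event table is still missing from the safety comparison.

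A reader might also infer that the whole safety comparison depends on a judgement about event numbers, because section 10 says: "If it is deemed that there are sufficient occurrences of adverse events in total, a formal test of significance will be performed". Only the Fisher test is conditional. Counts by group and per patient, and the split into serious and non-serious, are reported regardless, and section 10 acknowledges limited power. A request for further tables there would be a reporting preference, not a correction.

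**Conclusion.** The point holds as a defect in a definition, of moderate severity. As written, section 7.2.3 can be applied only after a choice that the SAP does not make, and neither choice gives the set of operated patients that section 6.3.3 implies. Grouping as randomised is explicit, and nothing else in the plan offsets it.

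The size is uncertain. One first-week death or withdrawal could change an arm from 4% to 0% if the week runs from surgery. One crossover would take less than one point off an assumed 20-point difference, and without crossovers the grouping rule has no effect. These figures rest on assumed counts at the planned 25 per arm. They also assume that section 10 uses the section 7.2.3 population, which is inferred from its name.

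Safety is a secondary and mainly descriptive objective. The primary endpoint, its ANCOVA and the Full Analysis Population are unaffected.

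**What to change.** Replace section 7.2.3 with a definition along these lines: the safety population is all randomised patients in whom the study operation was started, with no minimum time in the study, grouped by the operation actually received. Add one sentence to section 10 saying that the adverse event summaries, and the Fisher test if done, use this population. If any crossover occurs, an as-randomised summary may be added beside it, since grouping by operation received is no longer a purely randomised comparison.

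The cost is one paragraph and one sentence. No new data are needed: the operation received must already be known to form the per-protocol population in section 7.2.2, and the event window in section 6.3.3 stays as it is. Section 12.4 already provides for documented revisions. The change should be recorded there, with its reason, before the single final analysis.
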